[name], Ph.D, obtained his doctorate under [name], and has extensive experience and background in clinical TMS and taVNS, especially in the development of novel protocols for neurological disorders. His thesis work involves systematic elucidation of the dose response of taVNS on heart rate, use of heart rate as a biomarker of taVNS effect, and the use of taVNS with fMRI in determining pathways and regions affected by taVNS in adults. He determined that the 'on' pulse heart rate change was a mean of -3 beats per minute (bpm) while the 'off' pulse heart rate change was +6 bpm. Although these are statistically significant and measurable changes, they are physiologically insignificant. Nevertheless, this will be an important biomarker for infants, but is not expected to result in safety concerns. [name] careful and thorough studies lay the safety and efficacy groundwork for the current proposal.

D. RESEARCH DESIGN AND METHODS (including data analysis)

Due to the novelty of these studies, [name] will be present for each taVNS-paired feeding session conducted in the first participants, and as needed thereafter. [name] and or [name] will monitor taVNS effects. If any adverse events are noticed which are not described in the consent or are serious, we will inform the IRB before continuing with the next enrolled subject. Importantly, all of these methods have been done before, and published by our and other groups in adults, and we believe these extra precautions will assure the safety and well-being of any participants enrolled.

taVNS-paired feeding to enhance feeding behavior in neonates

Screening

Prospective participants will be identified by the PI ([name]) at the MUSC neonatal intensive care units (Level II and III), and checked for potential inclusion (please see the uploaded taVNS screening form). [name], and other clinical OTs based in the nursery may also mention the study to parents and refer them to [name] if they are interested in participating.

Participants

Inclusion criteria:

Infants must be clinically stable, on minimal respiratory support (nasal cannula, or room air), in discussions about Gtube placement for poor po feeding and are currently greater than or equal to 39 weeks post-menstrual age and

- 1) If born premature have been working on oral feeding for 30days;
or

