- 2) If term Infant with significant medical issues that have precluded oral feeding, such as hypoxic ischemic encephalopathy (HIE), have been working on oral feeding for 14days.

Exclusion criteria:

- 1) Unstable infants or those requiring respiratory support involving positive pressure.
- 2) Major unrepaired congenital anomalies
- 3) Anomalies/conditions that limit feeding volumes
- 4) Cardiomyopathy
- 5) Repeated episodes of autonomic instability (apnea or bradycardia) which are not self-resolving *

*Preterm infants commonly have short periods of shallow or absent breathing or lower heart rate termed apnea and bradycardia, respectively, and most are being treated for these physiologic manifestations of prematurity with caffeine, an effective central stimulant. Infants are on cardiorespiratory monitors through the nursery stay to capture events, many of which are self-resolving. Infants who require repeated episodes of tactile stimulation to come out of these events are defined as *unstable*.

Neonates who are beginning oral feeds after medical treatment for critical illnesses, such as HIE brain injury, will be included as these neonates represent a population in which taVNS-paired feeding could present the largest success in overcoming impaired brain development. Congenital syndromes may be included if the infants do not have major, unrepaired anomalies or anomalies that limit feeding volumes.

Written informed consent will be obtained from the mother if available and if she has custody or decision making authority for the participant, otherwise a parent or legal guardian, prior to participation in the experimental paradigm. Department of Social services may have custody of infant but require the parent or foster parent to consent for all medical procedures.

Electronic Consent will be used for situations when the parent (or Legally Authorized Representative) is at another hospital and cannot travel to MUSC to provide consent in person. We will use the approved REDcap system to obtain consent. [name] or other approved study personnel will go over the entire consent document on the phone with the parent to ensure comprehension and to confirm identity. Parent will be given a copy of the completed, signed consent form in person or by email or fax.

Study Design

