Safety Monitoring

Prior to determination of the daily sensory threshold of the infant, an initial pain level will be recorded using the NIPS. Previous studies using pain as a marker for safety in neonates check for pain halfway through the respective treatment (39-40). TENS treatments in studies examined in creating our protocol

typically lasted 30 minutes (41-43). Because the duration of the taVNS-paired feeding varies daily and will ultimately exceed 10 minutes, we will record pain levels before, at the end of treatment, and additionally at 5 and 10 minutes for longer sessions. This is shown in more detail in the *In Session Form* included.

In an effort to standardize delivery of taVNS-paired feeding treatment, the taVNS device will be placed in the left ear as default. Skin redness at the site of taVNS attachment to the ear is possible after treatment, but is expected to be transient. In order to prevent injury to the skin in contact with the device, each day the left ear will be first examined for redness prior to attaching the taVNS device. However, if there is skin redness at the site attachment to the ear prior to each day's treatment, we will switch the stimulation that day to the right ear. If these symptoms are persistent, we will decrease the stimulation.

ECG will be monitored during each treatment session. The HR measures will provide valuable data for safety analysis as well as immediate markers for physiological safety during taVNS-paired feeding. Bradycardia will be defined by NICU standards of <80bpm for 5 seconds.

In all sessions of taVNS-paired feeding, [name] or research staff trained in taVNS will be present. At any point during taVNS-paired feeding, the research staff will decrease stimulation intensity, if they feel the participant is in mild distress.

Developmental follow-up

Developmental follow-up is routine in all preterm and HIE infants, with clinical visits occurring every 3 months at Neonatal High-risk clinic. If parents do not bring their infants back for standard of care developmental testing, and if more convenient for parents, the developmental testing will be performed by Drs. [name] and/or [name] in the home or other location of the parent's choosing. Developmental testing in the home will be free of charge, and test information will be discussed with parents during the testing session and then uploaded into EPIC for other care providers.

Payment

No payment will be provided in this trial.

Data Analysis

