For safety we will compare HR changes from baseline to during taVNS within subjects. We will compare treatment before and after the taVNS-paired feeding treatment for the rate of feeding volume increase, and days to full po feeds. We will use repeated measures ANOVA to analyze repeated measures such as HR over 5 minutes and mean daily feeding volumes in 7-10 day epochs. We will analyze the number of infants who reach full feeds vs requiring G-tube during taVNS-paired feeding, between once and twice daily stimulation by Chi-squared. We will assess differences in kurtosis parameters from pre-to post taVNS scans by paired t-test, and between those that reach full oral feeds vs those that require a Gtube by unpaired t-test.

Estimated Difficulties, Limitations and Time Frames

Estimated Difficulties. Many of the initial parameters for taVNS in humans, such as frequency and pulse width, were accomplished in trials at MUSC by [name] et al. that were approved by the IRB. In one sense, we will be shrinking many of the components into miniature form to deliver stimulation to neonates and infants. In spite of the clear differences in size and skin between the neonatal and adult ear, the custom electrodes have been fitted to several different weights of infants (2.5-4.0 kg).

Limitations. We will not be delivering a SHAM stimulation paradigm (electrodes and Digitizer with appearance of taVNs treatment without actual current). Our goal is to determine safety and feasibility of active treatment with a dose response in order to investigate whether this should be administered in a larger randomized control trial. In this respect, the comparison we lose in not having a SHAM stimulation is offset by the validation we will receive in the safety and feasibility of active treatment. We will compare our overall results with characteristics of infants who required a Gtube from [name] and [name]'s publications.

Estimated Time Frames. The duration of the study will likely be ~4 years, with 2 years of active enrollment and 18 months of follow-up.

E. PROTECTION OF HUMAN SUBJECTS

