Not only does the current literature show a lack of harm done by tVNS, implantable cervical VNS also has a good safety record. According to Cyberonics, the company that supplies the cervical VNS implantable devices, there has been over 100,000 implanted patients being monitored by over 3,000 providing physicians. Most side effects range from alteration of voice, coughing, pharyngitis, hoarseness, headache, and nausea. Cardiac evaluations have been made on hundreds of VNS patients with no changes in cardiac function (Handforth et al, 1998; Sackeim et al, 2001b; Morris and Mueller, 1999) with long-term safety confirmed in recent large sample retrospective studies (Menascu et al, 2013; Ryvlin et al, 2014; Choi et al, 2013).

Bradycardia: [name] own safety studies in adults and this pilot study in infants designate a small, measurable change in heart rate which is not clinically significant (-3 and +6 bpm). Given the minimal risk of both of these already FDA approved methods, we intend to show that taVNS will continue to be a very safe procedure in neonates.

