2. ADEQUACY OF PROTECTION AGAINST RISKS

a. Recruitment and Informed Consent

This information is listed on the eIRB website.

b. Protection against Risk

The following risks are present with this study: Risk of skin irritation, risk of discomfort, risk of slightly decreased heart rate, and risk of loss of confidentiality.

Risk of skin irritation: we will monitor the skin on the inner aspect of the left ear before and after each session, and will switch to the right ear if redness is present, and decrease the stimulation if redness persists.

Risk of discomfort: We expect to be able to use the pain ratings scales to identify the perception of tingling versus pain with taVNS in these infants. We will use facial expression change, fidgety movements and infant behavioral discomfort using our standard neonatal pain scale (NIPS) with the bedside nurse at the start and after 5 minutes of taVNS, at 10 minutes and at the end of treatment. We will protect against the risk of discomfort by close monitoring and by the determination of perceptual threshold using the protocol outlined above.

We will hold the treatment for a NIPS score of >3 , until discomfort subsides, and resume at a lower stimulus level if this level of discomfort recurs. We do not expect the infant to cry at this level, but show discomfort in brow furrowing, grimace, etc. Feeding is generally comforting for infants, and we expect to see minimal pain response to treatment. Infants are fed sidelying in the nursery. We will position the baby so that the left ear is facing up, and we can monitor the site and pain without disturbing the feeding process unduly.

Risk of slightly decreased heart rate: we will monitor HR, respiratory rate and oxygen saturation continually during the feeding to monitor these physiologic responses to taVNS-paired feeding. The infants' vital signs are constantly monitored as standard of care while in the nursery. We will print out values at baseline, and changes with feeding and taVNS-paired feeding. Normal heart rate is 120-170 beats per minute in preterm infants feeding, and 110-140 bpm in term HIE infants. As HR usually accelerates with motor activity of feeding, we do not expect significant bradycardic HR changes during the 'on' pulse. However, if the HR decreases to <100 bpm during 'on' pulse, or if HR rebound is >190 bpm during 'off' pulse, we will hold treatment and start again at a lower stimulation level.

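### The only safety analysis in the Data Analysis section is a means-based heart-rate change; the bradycardia that the protocol defines has no planned count, rate or interval

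*Combined protocol and SAP*

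**What the plan says.** All references are to the combined protocol and SAP.

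- **Section D, Data Analysis.** The safety analysis is "For safety we will compare HR changes from baseline to during taVNS within subjects". The method follows: "We will use repeated measures ANOVA to analyze repeated measures such as HR over 5 minutes". No other safety analysis is listed.
- **Section D, Safety Monitoring.** On the purpose of the HR data: "The HR measures will provide valuable data for safety analysis as well as immediate markers for physiological safety during taVNS-paired feeding". An event definition comes next: "Bradycardia will be defined by NICU standards of <80bpm for 5 seconds". The definition is not used again.
- **Section E.2.b, Protection against Risk.** Treatment is held "if the HR decreases to <100 bpm during" the stimulus-on phase, or if the rebound exceeds 190 bpm in the off phase.
- **Section E.5, Data and Safety Monitoring Plan.** Adverse events are recorded as they happen. The IRB is told how many treatments were held for HR, redness or discomfort. The safety committee hears of every SAE at once, and data discussions are set after 5 and after 10 infants.
- **Section B, closing paragraph.** Safety and feasibility are the primary hypothesis; the hypotheses about infant improvement rank second.
- **Section C, Preliminary Studies.** For adults, the stimulus-on "heart rate change was a mean of -3 beats per minute (bpm"), with +6 bpm in the off phase. HR change is also to serve as a biomarker in infants.
- **Section E.1.c, paragraph on bradycardia.** The adult safety studies and "this pilot study in infants designate a small, measurable change in heart rate which is not clinically significant (-3 and +6 bpm").

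**The concern.** The cardiac risk of vagal stimulation is mainly one of episodes. Section E.1.c itself lists reduced heart rate and vasovagal syncope as theoretical risks. Repeated-measures ANOVA answers a different question: whether average HR shifts. A short fall in a few infants is diluted over the measurement window and again over the cohort, so the planned result would look much the same with or without such falls. The same average is also meant to show that the stimulus has an effect, so one quantity serves as both biomarker and safety result.

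The stake is the trial's stated purpose, which is to establish safety and feasibility before a larger randomized trial. As planned, the analysis would give that trial no estimate of how many infants have a defined bradycardia during stimulated feeds, and no upper limit on that proportion.

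**Working it through.** **Inputs from the document.** Up to 40 infants, single arm, 2 to 3 weeks of once- or twice-daily sessions (Study Design). HR window of 5 minutes, or 300 s (Data Analysis). Event: below 80 bpm for 5 s (Safety Monitoring). Normal HR of 120-170 bpm in preterm infants while feeding and 110-140 bpm in term HIE infants (E.2.b). Expected stimulus-on change of -3 bpm (Section C, adults).

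**Not given.** Significance level, power, SD of HR change, acceptable bradycardia rate, and any derivation of 40. There is no stated figure to reproduce. The lowest rates reached, durations, SDs and numbers of affected infants below are assumptions.

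**Step 1: dilution.** Shift in one infant's 5-minute mean = (baseline - lowest rate) x duration / 300.

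- 140 to 75 bpm for 5 s: 65 x 5 / 300 = 1.08 bpm. In the 40-infant mean: 1.08 / 40 = 0.027 bpm.
- A fall only just meeting the definition (to 79 bpm for 5 s): 31 x 5 / 300 = 0.52 bpm from 110, 61 x 5 / 300 = 1.02 from 140, and 91 x 5 / 300 = 1.52 from 170.
- Three such infants (multiply by 3/40): 0.04, 0.08 and 0.11 bpm, against an expected change of 3 bpm.

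**Step 2: would a test notice?** A paired t-test on 40 infants was simulated 20,000 times, with no other HR effect, as a simple stand-in for the ANOVA.

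| Assumed falls | Rejects, SD 5 bpm | Rejects, SD 10 bpm |
|---|---|---|
| None | about 5% | about 5% |
| 3 infants, 140 to 79, 5 s | 5.2% | 5.0% |
| 3 infants, 140 to 60, 15 s | 5.8% | 5.1% |
| 4 infants, 140 to 60, 30 s | about 11% | about 7% |
| 4 infants, 170 to 60, 30 s | about 16% | about 9% |

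For falls near the protocol's definition, the test behaves as if nothing had happened.

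**Step 3: can the hold tally stand in?** A fall below 80 bpm with the stimulus on is also below 100 bpm, so it should lead to a hold. The converse fails. Holds also include rates from 80 to 99 bpm, need no 5-second duration, and include rebounds above 190 bpm. Falls in the off phase are outside the low-HR hold rule. The tally is of treatments, with no denominator or interval stated. The number of infants with defined bradycardia cannot be recovered from it.

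**Step 4: what a count would give.**

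- 0 of 40: one-sided 95% upper limit 1 - 0.05^(1/40) = 7.2%; two-sided 1 - 0.025^(1/40) = 8.8%.
- Exact two-sided 95% limits: 1 of 40, 0.06% to 13.2%; 3 of 40, 1.6% to 20.4%.
- If the true per-infant risk is 5%, no affected infant is seen with probability 0.95^40 = 12.9%, so at least one is seen with probability 87.1%.
- At the scheduled data discussions, zero events gives one-sided upper limits of 45.1% (5 infants) and 25.9% (10 infants).
- Stimulated feeds: 40 x 14 x 1 = 560 to 40 x 21 x 2 = 1,680, but only with full enrolment, treatment every day and no early stopping. The actual number may be lower than 560.

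**The case against.** The strongest reply is that bradycardia is not ignored. Low HR with the stimulus on leads to a hold, holds are reported to the IRB, and adverse events are recorded in real time. Serious or unlisted events go to the IRB before the next infant is enrolled, and a committee reviews accumulating data with power to recommend stopping. A reader might infer from the Data Analysis section that bradycardia never reaches the safety conclusion. The documents do not support that, and these routes protect infants during the trial. They do not yield an estimate: Step 3 shows that the tally measures something else, and no data discussion is scheduled after 10 of up to 40 infants.

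Four other limits stand:

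- The Data Analysis section does not attach the word mean to HR. That reading follows from the choice of ANOVA.
- The protocol does not call its bradycardia definition serious, and it says that many apnea and bradycardia events in these infants resolve on their own. Background events are therefore expected.
- Five minutes is one sixth of a full 30-minute session but a larger share of a shorter one, so the window should not be described as always a small fraction.
- It is tempting to conclude that the infant figures of -3 and +6 bpm in E.1.c were simply carried over from adults. They do match, but part of Section C was not in the text available for this review, so infant data may be reported there. The match justifies asking for the source, not deleting the statement.

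**Conclusion.** The point holds as a gap in the analysis plan. The only planned safety analysis cannot show brief falls in a few infants, and the protocol's own bradycardia definition feeds no planned count, rate or interval. One assumed 5-second fall from 140 to 75 bpm moves the cohort mean by 0.03 bpm; three borderline falls move it by 0.04 to 0.11 bpm over baselines of 110 to 170 bpm. The dilution rests on assumed falls and the rejection rates on assumed SDs of 5 to 10 bpm. The exact limits need only the number of infants and the count.

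It does not follow that infants are unmonitored, or that the investigators would declare cardiac safety from a non-significant average; the plan does not say how the result will be interpreted. Because safety is part of the primary hypothesis, the plan should nevertheless state an event-based result.

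**What to change.** In Data Analysis:

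1. Make the main cardiac safety result the number and percentage of infants with at least one bradycardia, as defined under Safety Monitoring, during a stimulated feed, with an exact 95% CI.
2. Add events per stimulated feed, with an interval that allows for clustering by infant, and the number of feeds held for HR.
3. Where monitor records allow, show the event rate in the same infant's unstimulated oral feeds. This is descriptive only: those feeds are not randomized and may differ in feeder and conditions. The protocol says "Infants are on cardiorespiratory monitors through the nursery stay to capture events", but not that events are stored feed by feed, so retrievability should be checked first.
4. Keep HR change, with a CI, as the biomarker.

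In Safety Monitoring and E.2.b, reconcile the passages by stating how the bradycardia definition and the hold level relate in the safety summary. No threshold is proposed here. In E.1.c, ask the authors to confirm the source of the infant HR figures.

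The cost is a few sentences of analysis text and some extraction of monitor events. The safety statement also becomes less comfortable: even with no affected infant among 40, it is an upper limit of about 7 to 9%, and it is wider if fewer are enrolled.

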Feeding in neonates involves a sequence of sucking, swallowing, and breathing that requires coordination of the face, head, and neck muscles with the myelinated vagal regulation of the bronchi and the heart (11). In preterm neonates, the muscles needed to feed are underdeveloped, resulting in the need for OT rehabilitation to 'learn' feeding patterns. Preterm neonates' inability to feed effectively is the primary reason for prolonged hospital stays (12). In neonates with HIE, development of cortex and basal ganglia is interrupted, and depending on the severity, normal developmental plasticity is hindered, further contributing to their inability to feed (13). Both types of feeding difficulties involve complex motor learning, which requires integration of sensory and motor pathways. Treating oromotor difficulties during the learned task of feeding with noninvasive brain stimulation that promotes plasticity, poses a highly novel application of taVNS. Our major premise is that in babies at high risk for motor problems, simultaneously delivered brain stimulation via taVNS will boost motor cortical plasticity involved in a learned feeding task, leading to better feeding.

This protocol has 2 specific aims that will be investigated:

Specific Aim 1: Improved Motor Learning - We aim to investigate whether pairing taVNS with rehabilitation training of feeding behavior in preterm and HIE neonates will enhance and accelerate the learning of effective feeding behavior in a dose responsive manner. We call this treatment "taVNS-paired feeding." The primary outcome measures of taVNS-paired feeding will be daily oral milk feeding volume changes from before to during treatment, and number of infants reaching full oral feeds

between once and twice daily taVNS-paired feeding, duration to full feeds, as well as general motor functional impairment as measured by [name] Test of Early infant motor Performance (STEP). Our hypothesis is that taVNS-paired feeding for preterm neonates is feasible, safe and effective at reducing length of stay solely for feeding reasons, compared to historical controls. As part of our safety investigations with separate funding, we may perform taVNS during a clinical modified barium swallow study with pediatric speech language pathologists performing the study and compare 10 swallows with stimulation on and off to determine if taVNS affects swallowing parameters.

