Up to 40 preterm/HIE neonates will be enrolled in this prospective, open-label safety and feasibility trial, with a dose response. The experimental paradigm consists of 2 to 3 weeks of once or twice daily taVNS-paired feeding.

Our control group was investigated by Drs. [name] and [name] at MUSC, who have researched all infants failing feeding and getting Gastrostomy tubes in our nurseries over the past 5 years. We can compare our data to this historical group at our own institution.

All consented participants will receive the active stimulation condition.

taVNS Stimulation (in Detail)

After obtaining consent and describing this procedure to the parents and all members of the baby's care team, we will first, with a 500 μ s, 25Hz pulse, gradually increase the intensity of the TENS unit until the baby can first feel something in their ear. We will use the facial expression change and fidgety movements to determine when the infants feel the stimulation. This intensity will be recorded as the perceptual sensory threshold. The stimulation intensity we will use for this study on taVNS-paired feeding is a small decrement from the perceptual sensory threshold for each infant (-0.1mA), a point at which they should not react to the stimulation. We will retest the sensory threshold before every session.

Determination of Perceptual Threshold

1. Electrode clip will be placed on the left tragus in an enrolled infant at rest. Starting at 0.2mA at 25Hz, we will deliver 5 seconds of pulses, and increase by 0.1mA until the perceptual threshold is achieved by observation of the infant's facial expression, fidgety movements, or NIPPS score. This will be termed the perceptual threshold.
2. We will then deliver this level of microcurrent while the infant is feeding on the first day to determine if the perceptual threshold changes with feeding. Current will then be held constant while pulse width and frequency will be set at 500us and 25Hz, respectively.

3. Finally, we will decrease the microcurrent by 0.1mA *below the perceptual threshold* and administer this taVNS treatment during the feeding and deliver this only while the infant is actively sucking from the bottle.
4. The total duration of this 'on-and-off' taVNS stimulation treatment will continue for 30 minutes or the duration of the feed.
5. We may manually trigger the taVNS stimulation or place a gel EMG electrode over the temporomandibular joint area to trigger the taVNS impulse.

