1. RISKS TO THE SUBJECTS

The human subjects involved in this research will be preterm neonates or infants with critical illnesses that preclude oral feeding, such as HIE. Inclusion criteria involves 2 main groups. The first is comprised of typical pre-term, high risk neonates who are in the convalescent near and post-term period and learning to po feed. The second is comprised of neonates that present after severe medical illnesses or brain injury. In both cases, the infants can only be enrolled if they are stable, not making progress with OT training, and are in discussion for Gtube placement. Participants will be excluded if they have major unrepairs congenital abnormalities that limit volume of feeds, cardiomyopathy, significant autonomic instability, such as repetitive, unresolved bradycardia or apnea, or use a continuous positive airway pressure (CPAP) device or other form of high respiratory support preventing them from breathing without assistance.

Targeted/Planned Enrollment Table

Total Planned Enrollment: 40 babies (active)

TARGETED/PLANNED ENROLLMENT: Number of Subjects receiving active taVNS			
Ethnic Category	Sex/Gender		
	Females	Males	Total
Hispanic or Latino	4	5	9
Not Hispanic or Latino	15	16	31
Ethnic Category: Total of All Subjects*			

Racial Categories			
American Indian/Alaska Native			
Asian			
Native Hawaiian or Other Pacific Islander			
Black or African American	8	7	15
White	12	13	25
Racial Categories: Total of All Subjects*	20	20	40

*The “Ethnic Category: Total of All Subjects” must be equal to the “Racial Categories: Total of All Subjects”.

Volunteers of all ethnicities and racial categories will be accepted into this study protocol. No preference will be given based on race, gender or ethnicity. No vulnerable populations or special classes of subjects will be considered for participation.

b. Sources of Materials

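### Days to full oral feeds is planned as a before/after comparison, but no enrolled infant can have a 'before' value

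*Combined protocol and SAP*

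**What the plan says.** Data Analysis (section D) puts two feeding outcomes under one before/after comparison: "We will compare treatment before and after the taVNS-paired feeding treatment for the rate of feeding volume increase, and days to full po feeds". It gives no test, time origin, censoring rule or G-tube rule for this sentence. The next sentence plans a repeated measures ANOVA of mean daily volume in epochs of 7 to 10 days. A further sentence compares, by Chi-squared, the counts reaching full feeds or needing a G-tube between the two dose frequencies.

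On who enters, the inclusion criteria require infants to be "in discussions about Gtube placement for poor po feeding". A minimum history of oral feeding also applies. For preterm infants it reads "If born premature have been working on oral feeding for 30days"; term infants must "have been working on oral feeding for 14days". Risks to the Subjects (section E.1) adds that "the infants can only be enrolled if they are stable, not making progress with OT training, and are in discussion for Gtube placement".

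On the outcomes, Specific Aim 1 names "daily oral milk feeding volume changes from before to during treatment" and the number reaching full oral feeds. It then continues "between once and twice daily taVNS-paired feeding, duration to full feeds". Study Design sets a course of 2 to 3 weeks and states: "All consented participants will receive the active stimulation condition". It describes the historical comparison group as infants who failed feeding and received gastrostomy tubes.

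**The concern.** A before/after comparison needs a value of the same quantity on each side of treatment. Time to full oral feeds is a milestone that an infant reaches once or not at all. An infant who enters because oral feeding is poor has not reached it, so the 'before' side is empty. The 'after' side is empty for infants who receive a G-tube.

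This matters because duration to full feeds stands in the Aim 1 outcome sentence, and the Limitations paragraph says the results will inform whether a larger randomised trial should follow. An analyst given the present sentence would have to invent either a pre-treatment value or a different analysis after seeing the data.

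The rate of volume increase is a lesser matter. Pre-treatment data should exist for it, but the plan does not say which days form the baseline. Because entry requires lack of progress, the choice of days can influence the result.

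**Working it through.** The documents give no sample size, power or alpha for this comparison, so there is no planned figure to reproduce. The main check is one of logic.

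**1. Does a 'before' value exist?** Entry requires poor oral feeding with a G-tube under discussion. At first stimulation an infant has therefore worked on oral feeding for at least 30 days (preterm) or 14 days (term) without reaching full feeds. What is known is only that the time exceeds the days already spent. Infants with an observed pre-treatment time: 0 of up to 40.

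**2. Does an 'after' value exist?** Only for infants who reach full feeds. Data Analysis itself treats G-tube as the alternative outcome, and for those infants the time is never observed.

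**3. Can the historical group fill the gap?** No. As described, it consists of infants who failed feeding and received G-tubes, so it holds no times to full feeds to borrow.

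**4. What can be computed?** Time from first stimulation to full feeds, with G-tube as a competing event. The course lasts 14 to 21 days, so day 21 is a natural common horizon. If all infants are followed to that day, the exact (Clopper-Pearson) 95% intervals are:
- 20 of 40: 33.8% to 66.2%
- 10 of 20: 27.2% to 72.8%

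Both success counts are illustrative. Groups of 20 assume an equal split, which Study Design does not state.

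**5. Does the baseline window matter for the rate?**
- *Available history.* The minimum of 30 days holds 3 or 4 complete epochs (30/10 = 3; 30/7, rounded down, = 4). The minimum of 14 days holds 1 or 2 (14/10, rounded down, = 1; 14/7 = 2).
- *Precision.* With n independent daily values, the standard error of a fitted slope per unit of day-to-day SD is sqrt(12/(n(n² - 1))). This is 0.189 for n = 7, 0.110 for n = 10, 0.066 for n = 14 and 0.021 for n = 30. A 7-day slope is 0.189/0.110 = 1.7 times as uncertain as a 10-day slope.
- *Direction of bias.* If the baseline consists of the days on which lack of progress was judged, part of the flatness is chance. The next window will then tend to look steeper without any treatment effect. The size cannot be estimated from the documents. Against this, volume stops rising once full feeds are reached. If that happens a fraction f of the way through the window, the fitted slope is f²(3 - 2f) of the true slope: 0.84, 0.50 and 0.16 for f = 0.75, 0.50 and 0.25. The net sign is not fixed.

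**6. If a mixed model is used for the rate.** Assume a 10-day baseline, 14 treatment days, 40 infants and a day-to-day SD of 5 units. The variance of one infant's slope difference is 12×25/(10×99) + 12×25/(14×195) = 0.303 + 0.110 = 0.413. The 95% half-width is 2.02 × sqrt(0.413/40) = 0.21 units per day. If infants' true slope changes vary with an assumed SD of 0.5 or 1.0, add 0.25 or 1.00 to the variance. The half-width becomes 2.02 × sqrt(0.663/40) = 0.26 or 2.02 × sqrt(1.413/40) = 0.38. A model with only a random intercept and slope leaves this variation out and overstates its precision.

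**The case against.** The strongest reply is that this is loose drafting. The words on days to full feeds follow a comma and may not be meant to fall under the before/after comparison. Specific Aim 1 places duration to full feeds next to the once- versus twice-daily comparison, which can be computed. That reading is plausible, and it explains why the repair is small. It does not remove the problem, because Data Analysis is where the method is fixed and it states neither the origin nor the comparison.

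A second reply is that little rests on this outcome. Much of that stands. Success counts are compared separately by Chi-squared, and Limitations admits there is no sham. Background ranks efficacy behind safety and feasibility. Potential Benefits says G-tube avoidance cannot be determined here.

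A third reply concerns the volume baseline: lack of progress appears only in Risks to the Subjects, the formal criteria set no slope threshold, and the planned epochs give part of a window. This also stands, so the window is mostly a missing detail and is treated here as secondary.

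Two stronger readings are tempting. A reader might infer that the plan builds in a false benefit by setting at least 30 days already spent against a course of at most 21. Nothing in the documents proposes using time already spent as the 'before' value. A reader might also infer that the volume comparison is necessarily biased in favour of taVNS. The documents do not support that: the net sign of bias in the rate is open, and the lack of an untreated group is a limitation the protocol already admits.

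**Conclusion.** Wrong as written for days to full oral feeds: the before/after difference is undefined for all of the up to 40 infants, and the historical group cannot repair it. This follows from the entry criteria alone. The one assumption is that no infant had reached full oral feeds and then lost them before entry, a case the documents do not describe.

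For the rate of volume increase, the finding is only that no pre-treatment window is assigned. Data for one should exist. Regression to the mean is a real possibility given entry on lack of progress, but neither its size nor the net direction of bias can be stated from the documents.

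The point should be corrected before analysis. It does not undermine the safety and feasibility aim or the planned comparison of counts.

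**What to change.** 1. In Data Analysis, take days to full oral feeds out of the before/after sentence. Replace it with the cumulative incidence of full oral feeds, as defined by the sponsor, from first stimulation to one common day (for example day 21, the longest planned course). Treat G-tube as a competing event. Report it overall and by once- versus twice-daily group, alongside the planned Chi-squared comparison.
2. For the rate of volume increase, fix one pre-treatment window in days in advance. It should not rest only on the days used to judge lack of progress. Align the wording with Specific Aim 1, which says before to during, not before and after. State how days after full feeds or a G-tube are handled.
3. If a mixed model is used for the rate, include a random per-infant change in slope as well as a random intercept and slope.

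The cost is a short rewording and extraction of daily oral volumes that should already be in the clinical record. Sources of Materials does not name them, although the Aim 1 volume outcome already implies a baseline. The price in precision is plain: with up to 40 infants the incidence intervals will be wide, and the dose comparison wider still.
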